4.4.3.2 Missing Start and Stop Dates for Prior and Concomitant Medication

For the purpose of inclusion in prior and/or concomitant medication tables, incomplete medication starts and stop dates will be imputed as follows:

- If year and month are present and day is missing, then set day to first day of month for start date and set day to last day of month for end date.
- If year and day are present and month is missing, then set month to January for start date, and set month to December for end date.
- If year is present and month and day are missing, then set month and day to January 1 for start date and set month and day to December 31 for end date.
- Completely missing date will not be imputed.

The partial dates will be provided as such in the subject data listings (with the imputed dates).

When imputing a start date, the programmer will ensure that the new imputed date is sensible i.e. it is before the end date of prior and concomitant medications.

4.4.3.3

CCI

4.4.4 Concentrations Below the Limit of Quantification (BLQ)

For PK data, all concentrations that are BLQ will be labeled as “BLQ” in the concentration data listings (Footnote describing the BLQ value will be added to the listing).

For summary: For concentration summary tables and mean concentration time plots, all BLQs will be considered zero, and the number of BLQs and non-BLQs at each scheduled time point will be reported.

For individual data: For non-compartmental PK analysis, all below the limit of quantification (BLQ) values pre-dose to the first dose, and prior to the first quantifiable concentration will be substituted by zeros. BLQ values between non-BLQ concentrations will be considered missing before the calculation of the PK variables. Terminal BLQ values will be considered missing.

4.4.5 Adjustment for Multiplicity

No formal multiple statistical analyses are planned. Hence no adjustments for multiplicity are required.

4.4.6 Interim Analyses

No formal interim analyses are planned.

4.4.7 Unblinding

Part A is open-label.

Part B is double-blinded, such that study personnel (e.g., Investigators, site coordinators) and patients are blinded to treatment assignments and will remain blinded throughout the study.

Unblinded personnel include those involved in drug preparation and allocation (e.g., data systems support and pharmacists), and the study pharmacokineticist to allow for expedited review of PK data prior to SMC review.

The data for dose escalation in Part B will be presented and reviewed by the SMC in a blinded fashion. If required SMC will be unblinded as per SMC Charter and Blinded Maintenance Plan for Part B.

After completion of SMC review and once all patients in the cohort have completed the study, the sponsor study team members involved in biomarker data analysis may be unblinded to complete pharmacodynamic assessments as per Protocol section 4.4.

4.4.8 Final Analysis

The final analysis of the study data will be conducted once the last remaining patient has completed the study or is withdrawn from the study prior to completion, all data have been entered into the database, all data issues resolved, the protocol deviations have been addressed, and the database has been locked and released.

4.5 Software

All report outputs (tables, figures and listings) will be produced using SAS[®] version 9.4 or a later version in a secure and validated environment [1].

Non-compartmental PK analyses will be produced using Phoenix[®] WinNonLin (WNL) version [8.0] or a later version in a secure and validated environment [1].

All report outputs will be provided to the Sponsor in RTF and PDF format. Outputs will be printed in 8pt font size and Courier New font type.

4.6 Analysis Sets

Data for all subjects will be assessed to determine if subjects meet the criteria for inclusion in each analysis population in [Table 3](#). These analysis sets will be used to present the TLFs.

Table 3: Analysis Sets

Population	Description
All Treated Analysis Set (ATAS)	All patients who received any amount of study drug with treatment group based on the dose level received.
Pharmacokinetic Analysis Set (PKAS)	All patients who received at least one dose of KAN-101 and have at least one drug concentration value.
CCI	

The screened subjects are subjects who signed the ICF (including Screening failures). Enrolled subjects are the subjects who were enrolled in Part A or randomized for Part B and were not screen failures. PKAS and CCI are subsets of ATAS. PK analysis will be done on the PKAS

CCI

For Part A and Part B (separately and combined), summary tables will be provided by treatment group for analysis population shown in [Table 3](#) on enrolled subjects.

A by-subject listing will be provided by study part and treatment group for analysis population on enrolled subjects, unless otherwise specified in the table shells document.

4.7 Protocol Deviations

Protocol deviations are documented when the study protocol is not followed. Deviations from the protocol including violations of inclusion/exclusion criteria will be assessed as ‘minor’ or ‘major.’ Major protocol deviations are defined as those deviations from the protocol that are likely to have an impact on the subject’s right, safety, well-being, and/or the validity of the data for analysis. Minor deviations include all deviations from the protocol excluding those considered as major. Suggested Major/Minor protocol deviations are defined in study specific Protocol Deviation Specification.

All protocol deviations will be discussed during the Blinded Data Review Meeting (BDRM) per the applicable SOP between Parexel and Sponsor. An assessment will be made to determine whether any deviation warrants exclusion of a subject from descriptive statistical analyses. Decisions made regarding the exclusion of subjects and/or subject data from analyses will be documented in BDRM minutes and approved by the Sponsor (for more information on BDRM refer section [4.7.1](#)).

A by-subject listing will be provided by study part and treatment group for protocol deviations along with COVID-19 protocol deviations on enrolled subjects.

4.7.1 Blinded Data Review Meeting (BDRM)

A BDRM will be held after the last subject data is entered into the clinical database (DB) and prior to DBL. The primary purposes of the BDRM are to:

- Confirm that the database is ready to be hard locked.

- Agree on the assignment of each subject to the appropriate analysis sets of the study, if applicable.
- Identify any major/minor protocol deviation to finalize the analyses set.

Results and decisions made during the meeting will be summarized in BDRM minutes which will be signed off by Parexel representatives and the Sponsor.

The PKAS is decided at the PK data review meeting if needed, which occurs after the unblinded PK concentration data is received. For final analysis, the PK TLFs will be generated on the PK dataset created after data unblinding for Part B.

Parexel Protocol Deviation tool will be used to document the deviations.

4.8 Safety Evaluation

All safety summaries and analyses will be on ATAS.

4.8.1 Adverse Events

For Part A (SAD) and Part B (MAD) separately, the following AE summaries will be provided for the number of subjects reporting at least one AE by treatment group using the ATAS:

- An overall summary of TEAE will include the number of subjects with any TEAEs, drug-related TEAEs, \geq Grade 3 TEAEs, TESAEs, TEAEs leading to discontinuation (treatment and study);
- Before and after GC, overall summary of TEAE will include the number of subjects with any TEAEs, drug-related TEAEs, \geq Grade 3 TEAEs, treatment-emergent serious AEs (TESAEs), TEAEs leading to discontinuation (treatment and study); (this table is for Part B only);
- A summary of the number and percentage of subjects reporting a TEAE by system organ class (SOC) and PT;
- A summary of the number and percentage of subjects reporting a TEAE by causality, SOC and PT;
- A summary of the number and percentage of subjects reporting a TEAE by severity, SOC and PT.

AE summaries will be ordered in terms of decreasing frequency for SOC, and PT within SOC, in the Total group, and then alphabetically for SOC, and PT within SOC.

For each subject and each AE, the worst severity recorded will be attributed and used in the by-severity summaries. Similarly, the worst causality (most related to treatment) will be attributed and used in the by-causality summaries.

CCI

CCI

A summary of TESAE will be presented for Part A and B combined.

For Part A and Part B, by-subject listings of AEs will be presented by study part and treatment group for the following listings:

- All DLT events
- All TEAEs
- All SAEs
- All TESAEs
- TEAEs Leading to Study Discontinuation
- TEAEs Leading to Permanent Discontinuation of Study Drug

The following information will be included in the listings: verbatim (reported term), PT, SOC, AE onset date (and time), AE end date (and time), AE duration, relationship to study drug, AE outcome, severity and SAE indicator flag. If available, confirmed and suspected SARS-CoV-2 infections and/or COVID-19 cases will be recorded in the AE eCRF and data will be presented.

Pandemic related Impact of COVID-19 will be presented in listing, detailing the category of impact (example: Missed Visit, Missed Assessment, Early termination, Screen Failure, Adverse Event, Withdrawal of consent, Death, Replacement subject) based on data availability.

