The initial starting dose of KAN-101 in the Protocol version 2.0 was 1.5 mg/kg, a dose level consistent with an expected efficacious dose and supported by findings from the Good Laboratory Practice (GLP) toxicology studies. Due to non-serious adverse events observed in one patient at the 1.5 mg/kg dose level, the protocol has been amended to start at the dose of 0.15 mg/kg, 10-fold lower than the dose which induced symptoms consistent with gluten ingestion in celiac patients.

Part A will use a 3+3 design to evaluate escalating single doses of KAN-101. Approximately 12 to 24 patients are anticipated for enrollment in Part A. At any dose level, if none of the first 3 patients experiences a dose-limiting toxicity (DLT) (defined as any \geq Grade 3 AE assessed as related to KAN-101 or any Grade 2 AE assessed as related to KAN-101 not resolving within 14 days) then escalation to the next dose level may proceed if recommended by the SMC and approved by the Sponsor. If 1 of the first 3 patients experiences a DLT, the dose level will expand to a maximum of 6 patients if recommended by the SMC. If no DLT occurs among the 3 additional patients enrolled at that dose level, then escalation to the next dose level may proceed if recommended by the SMC and approved by the Sponsor.

Any DLT experienced during the study will result in study pause and review by the SMC. Any \geq Grade 4 AE will result in notification of the FDA in parallel with the SMC and study dosing and enrollment will be paused pending review by FDA. The non-tolerated dose (NTD) is the dose level at which 2 or more patients experience a DLT during the dose escalation safety monitoring period. The maximum tolerated dose (MTD) will be defined as the dose level immediately below the NTD. Of note, dose escalation may not identify an NTD or MTD.

Safety Monitoring Committee

This study will utilize an SMC that will meet regularly to review all accumulated data, including safety and PK (when available) during dose escalation. The SMC will recommend all dose escalation decisions, and/or any changes to the dosing paradigm based on review of the received data. The SMC will also make recommendations about the dose(s) selected for Part B. The Sponsor will make all final decisions related to the doses and regimens examined in this study.

Inclusion Criteria

1. Adults aged 18 to 70 years inclusive

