Patients will return to the clinic on D15 to initiate oral GC and on D21 for biomarker sample collection. Blood and serum samples will be collected for PK, PD, and ADA assessments during Part B of the study. Patients in Part B may be replaced if they do not receive the full 3 doses of

study drug or do not complete the D21 visit, as long as the discontinuation was not due to a DLT assessed to be related to study drug. In the event that patients are unable to return to the clinic for protocol-specified visits, alternative methods for safety assessments and data collection may be employed to ensure the safety of the trial participant where appropriate.

To assess the PD effects of KAN-101, on D15 of Part B patients will begin a 3-day, self-administered high-dose (9 g of gluten protein) oral GC. Typically, a 3-day oral GC is not long enough to induce changes in GI histopathology, and reactions are limited to mild or moderate symptoms. Any severe symptoms experienced by patients during the GC will be treated as medically indicated. To ensure patient safety, patients with a history of hyperacute symptomology or prolonged symptoms after gluten exposure will be excluded from Part B.

The GC is positioned 1 week after the last dose to allow sufficient time for T cell tolerance induction to develop. The initial dose of the GC will be administered in the clinic, and patients will be monitored for at least 6 hours post gluten administration [REDACTED]. GC administration on D16 and D17 will be self-administered at home, at approximately the same time as the first in-clinic administration.

[figure not shown]
CCI

Based on data obtained during both the SAD and MAD parts of the study, the protocol may be amended to explore additional higher dose levels and dosing schedules if supported by the data, recommended by the SMC, and approved by the Sponsor.

Please see [Table 2](#) for the complete schedule of assessments for Part B.

Figure 1: Overview Study KAN-101-01

Single Ascending Dose (SAD): 3 patients will be dosed IV with KAN-101. Initiation of the next dose cohort will commence once all patients in a cohort reach D8 postdose, and upon acceptable safety review by SMC and approval from Sponsor.

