6.1.11. Gluten Challenge

All patients enrolled in Part B of the study will undergo a GC for 3 days, from D15 to D17. During these 3 days, patients will self-administer 9 g of gluten protein orally (PO) once each day at approximately the same time every morning. The first dose of gluten will be administered in the clinic, and the patient will be observed for at least 6 hours to monitor for hyperacute reactions requiring medical treatment and collection of biomarker samples. Patient compliance will be recorded by the study Investigator.

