3.5.1.1 Adverse Events (AE)

All AEs from the time of signing of Informed Consent Form (ICF) through the final Follow-Up Visit/phone call will be collected. Adverse events will be coded using the Medical Dictionary for Regulatory Activities (MedDRA) Version 23.1 (MedDRA Sep 2020) or higher. Ongoing AEs considered at least possibly related to KAN-101 treatment should be followed until resolution, return to baseline, or are considered stable or chronic.

AE:

An AE is defined as any untoward medical occurrence associated with the use of a drug, or with study participation, whether or not consider related to study treatment.

TEAE:

TEAEs are defined as AEs that emerge or worsen in the period from the first dose of study treatment to the final Follow-Up Visit/phone call after the last dose study drug.

The incidence and severity of TEAEs as assessed by the CTCAE v5.0 or higher is considered the primary endpoint. TEAEs that occur before and after gluten challenge will also be examined separately and defined as in section 4.8.1.

DLT:

A dose-limiting toxicity (DLT) for Study KAN-101-01 is defined as any \geq Grade 3 AE assessed as related to KAN-101 or Grade 2 AE assessed as related to KAN-101 not resolving within 14 days. DLTs do not include those AEs attributable solely to intercurrent illness or other concomitant medications.

AE Severity:

The National Cancer Institute Common Toxicity Criteria Adverse Event (NCI-CTCAE) version 5.0 or higher will be used to grade the severity of all AEs, whether or not they are considered related to KAN-101. Toxicities that are not specified in the NCI-CTCAE will be defined as follows:

- Grade 1: Mild; asymptomatic or mild symptoms; clinical or diagnostic observations only; intervention not indicated
- Grade 2: Moderate; minimal, local or noninvasive intervention indicated; limiting age-appropriate instrumental activities of daily living (ADL)
- Grade 3: Severe or medically significant but not immediately life-threatening; hospitalization or prolongation of hospitalization indicated; disabling; limiting self-care ADL
- Grade 4: Life-threatening consequences; urgent intervention indicated
- Grade 5: Death related to AE

AE Causality:

Relationship to the study drug for all AEs will be assessed as “drug related” (Possible, Probable, Definite) or “not drug related” (None, Remote).

Impact of COVID-19:

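### Part B: in the visible SAP, only the overall TEAE summary is split at the gluten challenge, so the SOC/PT, causality and severity tables mix post-drug with post-gluten events

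*SAP*

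**What the plan says.** SAP 3.5.1.1 sets the endpoint: "The incidence and severity of TEAEs as assessed by the CTCAE v5.0 or higher is considered the primary endpoint". It defines TEAEs as "AEs that emerge or worsen in the period from the first dose of study treatment to the final Follow-Up Visit/phone call", which in Part B means from D1 to the D28 call. Protocol 6.1.11 places the challenge inside that window, for active and placebo patients alike: "All patients enrolled in Part B of the study will undergo a GC for 3 days, from D15 to D17".

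The SAP recognises the issue. Section 3.5.1.1 adds: "TEAEs that occur before and after gluten challenge will also be examined separately and defined as in section 4.8.1". Section 4.8.1 then lists one split output, for Part B only: "Before and after GC, overall summary of TEAE will include the number of subjects with any TEAEs", followed by drug-related, Grade 3 or higher, serious, and discontinuation TEAEs.

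The next three outputs carry no period qualifier. They are "A summary of the number and percentage of subjects reporting a TEAE by system organ class (SOC) and PT" and the matching tables by causality and by severity. The rules that assign one worst severity and one worst causality per subject and event also have none.

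Two blocks of 4.8.1 are redacted, and the before/after definition promised in 3.5.1.1 does not appear in the visible text.

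**The concern.** The symptoms already seen with KAN-101 are of the kind that the challenge provokes. The protocol synopsis explains the present starting dose as "10-fold lower than the dose which induced symptoms consistent with gluten ingestion in celiac patients". Protocol 1.2 also reports nausea, abdominal pain and vomiting in some patients given an adjuvant-free, non-targeted peptide mix. Drug effect and challenge effect can therefore fall under the same preferred terms.

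In an unsplit table a patient counts once per term, so nausea after D15 hides whether nausea also occurred between D1 and D15. Under the worst-severity rule, a Grade 2 event after gluten replaces a Grade 1 event after drug.

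The planned overall split does not fill this gap. It names no symptom, and its only severity cut is Grade 3 or higher, whereas Protocol 4.2 says of a 3-day challenge that "reactions are limited to mild or moderate symptoms". At stake is a readable account of which symptoms follow repeated dosing, and at what grade, in the only placebo-controlled, multiple-dose part of the study.

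**Working it through.** **The plan's own figure.** SAP 3.2 states power of 0.80 to detect an AE with event rate 0.25 in 6 active patients. Read as the chance of seeing at least one event, this is 1 - 0.75^6 = 0.822. With 5 patients it is 1 - 0.75^5 = 0.763. Six is thus the smallest number that reaches 0.80. The figure is a detection probability, not a comparison with placebo. I use the rate of 0.25 below.

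**Inputs.**
- Part B size: 18 active and 6 placebo (SAP 3.2).
- Pre-challenge rate of a given term: d = 0.25 on active, borrowed from the plan's event rate, and b = 0 on placebo (assumption; b = 0.10 as a variant).
- Fraction with that term after gluten: g. The documents give no value, so I assume 0.2 to 0.9, equal in both arms and independent of pre-challenge events.

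**Formula.** Full-window incidence is 1 - (1-d)(1-g) on active and 1 - (1-b)(1-g) on placebo. The difference is (d-b)(1-g).

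| g (assumed) | Active | Placebo | Difference (points) | Expected counts, of 18 vs of 6 |
|---|---|---|---|---|
| Pre-challenge only | 25% | 0% | 25 | 4.5 vs 0 |
| 0.2 | 40% | 20% | 20 | 7.2 vs 1.2 |
| 0.4 | 55% | 40% | 15 | 9.9 vs 2.4 |
| 0.6 | 70% | 60% | 10 | 12.6 vs 3.6 |
| 0.8 | 85% | 80% | 5 | 15.3 vs 4.8 |
| 0.9 | 92.5% | 90% | 2.5 | 16.65 vs 5.4 |

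With b = 0.10, the pre-challenge difference of 15 points becomes 15(1-g): 12, 9, 6, 3 and 1.5 points.

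**Direction.** With b = 0, the binomial chance that the observed active rate (of 18) exceeds the observed placebo rate (of 6) is 0.99 before the challenge. In the unsplit table it is 0.81, 0.70, 0.62 and 0.52 at g = 0.2, 0.4, 0.6 and 0.8.

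**Unequal g.** If the drug reduces gluten reactions, the sign can turn. With assumed g of 0.4 on active and 0.6 on placebo, the full-window rates are 1 - 0.75 × 0.6 = 55% and 60%.

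**Whether a split would be clean.** SAP 3.5.5.5 captures dates and times of gluten intake, so a cut at the first gluten dose is possible. SAP 4.4.3.1, however, sets an unknown AE time to 00:00 for tabulations, which puts an untimed D15 reaction before the in-clinic gluten dose. A wholly missing onset date, or one with only the day missing in the month of first dose, becomes the first-dose date. Both rules can move post-gluten events into the pre-challenge period.

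**The case against.** - **Redaction.** The missing definition, and perhaps further split tables, may sit in the redacted blocks of 4.8.1. This stands. The point covers visible text only and the fix is conditional.
- **Planned separation.** A reader might infer that gluten symptoms mask the primary endpoint as a whole, or that the study cannot tell whether KAN-101 causes these symptoms. The documents do not support that. The before/after summary gives any, drug-related, Grade 3 or higher, serious and discontinuation TEAEs by period. Listings give term, severity, relationship and onset date and time for 24 patients. What is lost is tabulated detail by term and at Grade 1-2.
- **Escalation.** A reader might infer that dose escalation rests on contaminated data. It does not: under Protocol 4.7 the Part B monitoring period ends on D15 before the challenge, and Protocol 12.6 limits the Part B DLT analysis to D1 to D15.
- **Part A.** It has no challenge and uses the same three dose levels as Part B plus 1.2 mg/kg. That helps, but it is single-dose and has no placebo.
- **Causality assessment.** Investigators weigh other causes, yet Protocol 11.2.2 counts a Possible event as drug-related even where another cause may exist. The help is partial.
- **Size.** No g is given, and Part B excludes patients with hyperacute or prolonged gluten reactions. At g = 0.2 the loss is only 5 points. One placebo patient is 1/6 = 16.7 points, so much of the dilution is below the resolution of the data. This stands, and limits the weight of the point.

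**Conclusion.** The point holds in a limited form. On the visible text, the SOC/PT, causality and severity tables for Part B, and the worst-severity and worst-causality rules, run across the gluten challenge. Those tables cannot separate post-drug from post-challenge events by preferred term or at Grade 1-2.

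Under the assumptions above (equal g in both arms, independence, 25% against 0% before the challenge), a 25-point difference appears as 20 to 2.5 points for g from 0.2 to 0.9. The range is illustrative, because g is not in the documents. The study is descriptive with no hypothesis test, so the harm is to interpretation and not to error rates.

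It does not follow that pre-challenge tables should displace the full-period ones. The TEAE window runs to final follow-up, and late drug effects or an altered response to gluten are safety information too.

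**What to change.** Unless the redacted text of SAP 4.8.1 already provides it:

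1. Repeat the three Part B tables (SOC/PT, causality, severity) for onset before and after the first gluten dose, by dose and pooled placebo, alongside the full-period tables.
2. In the period tables, derive worst severity and worst causality within period.
3. Define the cut visibly as the actual time of the first gluten dose on D15.
4. State how D15 events with no recorded time, and events with partial or missing onset dates, are assigned. One option is a separate line for events whose period cannot be determined, so that the 00:00 and first-dose-date imputations do not settle it by default.

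Cost: three repeated tables, using a period flag that the overall before/after summary already needs, plus a few sentences of definition. Counts per cell will be small and should be read as description only.
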